Though there are no statistically powered hypotheses, the overall study cohort of 3080 subjects will provide a probability of approximately 95% of observing any AE with a true incidence of 0.15%. In the treatment arm with 2310 subjects, there is a probability of approximately 95% of observing any AE with a true incidence of 0.2%.

Table of Study Procedures

	Phase III Study, 5 Visits, 4	Vaccination visits, 6 Tele	ephone calls, 18 Vaccinations,	16-Months' Duration Per Subject
--	------------------------------	----------------------------	--------------------------------	---------------------------------

Visit/Contact	Visit 1	Telephone Call (TC) 1	Visit 2	TC2	Visit 3*	ТС3	TC4	Visit 4†	TC5	Visit 5	TC6 Follow-up contact
Approximate age of subject	2 months (42 to 89 days)	-	4 months	-	6 months (164 to 224 days)	-		12 months	-	13 months	18 months
Trial timelines (days)	D0	Visit 1 + 8 days	Visit 1 + 60 days	Visit 2 + 8 days	Visit 2 + 60 days	Visit 3 + 8 days	Visit 4 -14 days		Visit 4 + 8 days	Visit 4 + 30 days	Visit 4 + 180 days
Time windows (days)		+2 days	+14 days	+2 days	+14 days	+2 days			+2 days	+21 days	+30 days
Informed consent form signed and dated	Х										
Inclusion/exclusion criteria	Х										
Collection of demographic data	Х										
Medical history	Х										
Physical examination	Х							Х			
Temperature measurement	Х		Х		Х			Х			
Contact IRT system for randomization / allocation of subject number / vaccine group assignment	Х										
Review of warnings and precautions to vaccinations	Х		Х		Х			X			
Review of contraindications to subsequent vaccinations and conditions for withdrawal‡			X		X			X			

Sanofi Pasteur 395 - MenACYW Conjugate Vaccine

Visit/Contact	Visit 1	Telephone Call (TC) 1	Visit 2	TC2	Visit 3*	TC3	TC4	Visit 4†	TC5	Visit 5	TC6 Follow-up contact
Contact IRT system for dose allocation for all vaccines			Х		Х			Х			
Vaccination with MenACYW conjugate vaccine or MENVEO [®]	X		X		X			X			
Vaccination with routine pediatric vaccines§	X		X		X			X			
Immediate surveillance (30 minutes)	Х		Х		Х			Х			
Diary card (DC) provided	DC1		DC2		DC3			DC4			
Telephone call		X**		X**		X**	X††		X**		X‡‡
Diary card reviewed and collected			DC1		DC2			DC3		DC4	
Recording of solicited injection site and systemic reactions§§	Х		Х		Х			Х			
Recording of unsolicited AEs					Recorded fro	m D0 to D30	after each vac	cination visit			
Reporting of SAEs (including AESIs) and MAAEs ***					To be re	eported throug	hout the study	y period			

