Collection of reportable concomitant medications	Х		Х		Х			X		X	
Memory aid (MA) provided										MA†††	
Trial termination record (termination of active portion of the trial)										Х	

* At Visit 3, subjects must be at least 24 weeks of age (the minimum age for the last dose of hepatitis B vaccine) and no more than 32 weeks of age (the maximum age for the last dose of rotavirus vaccine).

† At Visit 4, subjects must be 12 months of age, (from the day subjects turn 12 months of age until the day before turning 13 months of age).

‡ Physical examination should be performed on the basis of relevant medical history at the time of the visit according to the Investigator's clinical judgment. Temperature needs to be measured before each vaccination and recorded in the source documents.

- § Routine pediatric vaccines at Visit 1: Pentacel[®], PREVNAR 13[®], RotaTeq[®], ENGERIX-B[®]; at Visit 2: Pentacel[®], PREVNAR 13[®], and RotaTeq[®], and RotaTeq[®]; at Visit 3: Pentacel[®], PREVNAR 13[®], RotaTeq[®], and ENGERIX-B[®]; at Visit 4: PREVNAR 13[®], M-M-R[®] II, and VARIVAX[®].
- ** This call is made 8 days after the respective vaccinations. If D08 falls on a weekend or holiday, the telephone call may be made on the following business day. During this telephone call, the staff will find out whether the subject experienced any SAE (including AESIs) and / or MAAE not yet reported, and will remind the subject's parent / guardian to continue using the diary card, to bring the diary card to the study center at the next visit, and confirm the date and time of the next visit.
- †† Staff will contact the subjects' parent/ guardian by telephone within 14 days before Visit 4 (any time between 14 days and 1 day before Visit 4) to remind them about the forthcoming study visit. If the subject's participation in the study is discontinued, the information recorded on the diary card will be reviewed at this time and the subject's parent / guardian will be asked to mail the diary card to the site.
- \$\$\frac{1}{2}\$ Staff will contact the subject's parent/ guardian by telephone at 6 months (+ 30 days) after the last vaccination visit to identify the occurrence of any SAEs (including any AESIs) and MAAEs not yet reported. The final telephone call will continue until contact is made or 28 days have passed at which time the subject will be considered lost to follow-up.

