3.2 Study Plan

The schedule of assessments and study vaccinations is provided in the Table of Study Procedures (Table 3.1) and Table of Vaccination Schedule (Table 3.2).

^a First dose of hepatitis B vaccine must be given at least 28 days prior to study enrollment.

Vaccination

All subjects will receive a dose of either MenACYW conjugate vaccine or MENVEO® with routine pediatric vaccines at 2, 4, 6, and 12 months of age. All subjects will receive the routine pediatric vaccines at the approved ACIP recommended schedules: Pentacel® at 2, 4, and 6 months of age³; PREVNAR 13® at 2, 4, 6, and 12 months of age; RotaTeq® at 2, 4, and 6 months of age; ENGERIX-B® at 2 and 6 months of age³; and M-M-R® II and VARIVAX® at 12 months of age.

Study vaccines will be administered according to the following schedules:

Group 1: MenACYW conjugate vaccine and routine pediatric vaccines will be administered at 2, 4, 6, and 12 months of age.

Group 2: MENVEO® vaccine and routine pediatric vaccines will be administered at 2, 4, 6, and 12 months of age.

Blood sampling

No blood samples will be collected as this is a safety study.

Collection of safety data

- All subjects will be followed for safety from Visit 1 to 6 months after the last vaccinations at 12 months of age.
- All subjects will be observed for 30 minutes after each vaccination, and any unsolicited systemic AEs occurring during that time will be recorded as immediate unsolicited systemic AEs in the case report book (CRB).
- The subject's parent / guardian will record information in a diary card about solicited reactions from D0 to D07 after each vaccination and unsolicited AEs from D0 after each vaccination to the next study visit.
- SAEs (including AESIs) and MAAEs will be recorded throughout the study. The subject's parent / guardian will record information in a diary card about SAEs and MAAEs from Visit 1 to Visit 2, from Visit 2 to Visit 3, from Visit 3 to Visit 4, and from Visit 4 to Visit 5. SAEs and MAAEs will also be recorded in a memory aid from D31 after the last vaccination visit until the 6-month follow-up phone call.
- The subject's parent/ guardian will be asked to notify the site immediately about any potential SAEs at any time during the trial.

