Medical history	X										
Physical examination	X							X			
Temperature measurement	X		X		X			X			
Contact IRT system for randomization / allocation of subject number / vaccine group assignment	X										
Review of warnings and precautions to vaccinations	X		X		X			X			
Review of contraindications to subsequent vaccinations and conditions for withdrawal‡			X		X			X			
Contact IRT system for dose allocation for all vaccines			X		X			X			
Vaccination with MenACYW conjugate vaccine or MENVEO®	X		X		X			X			
Vaccination with routine pediatric vaccines§	X		X		X			X			
Immediate surveillance (30 minutes)	X		X		X			X			
Diary card (DC) provided	DC1		DC2		DC3			DC4			

Visit/Contact	Visit 1	Telephone Call (TC) 1	Visit 2	TC2	Visit 3*	тсз	TC4	Visit 4†	TC5	Visit 5	TC6 Follow- up contact
Telephone call		X**		X**		X**	X††		X**		X‡‡
Diary card reviewed and collected			DC1		DC2			DC3		DC4	
Recording of solicited injection site and systemic reactions§§	X		X		X			X			
Recording of unsolicited AEs			Recorded from D0 to D30 after each vaccination visit								
Reporting of SAEs (including AESIs) and MAAEs ***			To be reported throughout the study period								
Collection of reportable concomitant medications	X		X		X			X		X	
Memory aid (MA) provided										MA†††	
Trial termination record (termination of active portion of the trial)										X	

^{*} At Visit 3, subjects must be at least 24 weeks of age (the minimum age for the last dose of hepatitis B vaccine) and no more than 32 weeks of age (the maximum age for the last dose of rotavirus vaccine).

- † At Visit 4, subjects must be 12 months of age, (from the day subjects turn 12 months of age until the day before turning 13 months of age).
- ‡ Physical examination should be performed on the basis of relevant medical history at the time of the visit according to the Investigator's clinical judgment. Temperature needs to be measured before each vaccination and recorded in the source documents.
- § Routine pediatric vaccines at Visit 1: Pentacel®, PREVNAR 13®, RotaTeq®, ENGERIX-B®; at Visit 2: Pentacel®, PREVNAR 13®, and RotaTeq®; at Visit 3: Pentacel®, PREVNAR 13®, RotaTeq®, and ENGERIX-B®; at Visit 4: PREVNAR 13®, M-M-R® II, and VARIVAX®.

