4.1.1.3.5 Medically-Attended Adverse Events

MAAE information will be collected throughout the study. MAAEs will be recorded as unsolicited AEs for up to D30 after each vaccination and as MAAEs until the next study visit on the appropriate diary cards. MAAEs that occur from D31 after the last vaccination visit until the 6-month follow-up phone call will be recorded in the appropriate memory aid. An MAAE that occurs within the study period but meets the definition of an SAE should be reported only on the SAE Reporting Form but not on the MAAE page of the CRB.

The Investigator will assess the causal relationship between the MAAE and the investigational or study product as either "Not related" or "Related", as described in Section 4.1.1.3.6.

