4.2.1.3 SAEs (including AESIs)

An event will be considered as a serious event if "Yes" is checked for "Serious" in the CRF.

An event will be considered as an AESI if "Yes" is checked for "Is the event an AESI?" in the CRF.

SAEs (including AESIs) will be analyzed throughout the study using the following periods:

- Within 7 days after vaccination
- Within 30 days after vaccination
- During the study (i.e., all SAEs occurred during the study), including the 6-month follow-up period

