4.2.1.4 Medically-Attended Adverse Event (MAAE)

An event will be considered as an MAAE if "Yes" is checked for "Is the event an MAAE?" in the CRF.

MAAE will be analyzed during the following time periods:

- Within 7 days after vaccination
- Within 30 days after vaccination
- During the study (i.e., all MAAEs occurred during the study), including the 6-month follow-up period.

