AEs leading to study discontinuation	D0 to D30 after each vaccination in Group 1 and Group 2; D31 to next visit after each vaccination in Group1 and Group 2; During the whole study in Group 1 and Group 2	Percentage of subjects that have the event, MedDRA terms, time of onset, duration, intensity, relationship, action taken, outcome, study discontinuation
SAE (including AESI)	D0 to D7 after each vaccination in Group1 and Group 2; D0 to D30 after each vaccination in Group1 and Group 2; D31 to next visit after each vaccination in Group1 and Group 2; During the whole study in Group1 and Group 2	Percentage of subjects that have the event, MedDRA terms, time of onset, duration, relationship, seriousness criteria, outcome, study discontinuation
MAAE	D0 to D30 after each vaccination in Group 1 and Group 2; D31 to next visit after each vaccination in Group1 and Group 2; During the whole study in Group 1 and Group 2	Percentage of subjects that have the event, MedDRA terms, time of onset, duration, intensity, relationship, action taken, outcome, study discontinuation

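### The Visit 3 age row starts at 164 days, 4 days below the 24-week minimum in its own footnote (minor error); after dose 4, a clearer late interval in SAP Table 5.2 would be a cheap improvement

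*Protocol*

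**What the plan says.** **Visit 3 age.** In the protocol's Table of Study Procedures and in SAP Table 3.3, the approximate-age row gives Visit 3 as "6 months (164 to 224 days"). The Visit 3 column header carries an asterisk. The protocol footnote reads: "At Visit 3, subjects must be at least 24 weeks of age (the minimum age for the last dose of hepatitis B vaccine"). It goes on to set an upper limit of 32 weeks, the maximum age for the last rotavirus dose. The SAP repeats the footnote: "At Visit 3, subjects must be at least 24 weeks of age". ENGERIX-B is among the vaccines given at Visit 3 (protocol Table 5.1).

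**Late events after dose 4.** SAP Table 5.2 lists, for SAEs (including AESIs) and for MAAEs, an interval of "D31 to next visit after each vaccination in Group1 and Group 2". SAP 3.2 describes collection after the last dose as follows: "SAEs and MAAEs will also be recorded in a memory aid from D31 after the last vaccination visit until the 6-month follow-up phone call". SAP 4.1.1.3.5 says the same for MAAEs: "MAAEs that occur from D31 after the last vaccination visit until the 6-month follow-up phone call will be recorded". The SAP's whole-study analysis period covers this time, for SAEs (4.2.1.3: "During the study (i.e., all SAEs occurred during the study), including the 6-month follow-up period") and for MAAEs (4.2.1.4: "During the study (i.e., all MAAEs occurred during the study), including the 6-month follow-up period").

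**Visit 5 window.** Protocol section 5.1.4 and the protocol table allow 30 (+21) days after Visit 4. SAP Table 3.3 gives +14 days.

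**The concern.** The age row and its footnote sit in the same table and state the same limits in different units. They agree to the day at the upper end and disagree at the lower end. Protocol 5.2.7.1 sends sites to this table for the permitted vaccination timeframe, and the Visit 3 steps in 5.1.4 do not repeat the minimum age, although the Visit 4 heading does state its age requirement. If a site scheduler or a programmed window check used 164 days, an infant could receive the last hepatitis B dose before the plan's own minimum age.

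The Table 5.2 point concerns reporting. After doses 1 to 3 the next visit is the next vaccination, so D0 to D30 plus D31 to next visit covers all of the follow-up to the next dose. After dose 4 the next visit is Visit 5, about a month later, while SAEs and MAAEs are collected for about 6 months. Describing safety is the trial's only objective, and a reader of the report may want to see the late period after the last dose on its own.

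**Working it through.** **1. Visit 3 age limits**

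Inputs: row 164 to 224 days; footnote 24 to 32 weeks; entry age 42 to 89 days; Visit 2 at Visit 1 + 60 (+14) days; Visit 3 at Visit 2 + 60 (+14) days.

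- Upper limit: 32 × 7 = 224. The row's figure is reproduced.
- Lower limit: 24 × 7 = 168. The row says 164, which is 23 weeks 3 days. Gap: 168 − 164 = 4 days.
- The visit schedule does not explain 164 either. Its minimum is 42 + 60 + 60 = 162 and its maximum is 89 + 74 + 74 = 237. Two 61-day steps would give 42 + 122 = 164, but the schedule uses 60 days, and the documents do not say where 164 comes from.

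Which infants can be 164 to 167 days old at Visit 3 with both visits in window? Age at Visit 3 = entry age + 120 + extra days, where extra days run from 0 to 14 + 14 = 28.

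| Entry age (days) | Earliest Visit 3 age | Extra days giving 164–167 | Extra days needed for 168 |
|---|---|---|---|
| 42 | 162 | 2–5 | 6 |
| 43 | 163 | 1–4 | 5 |
| 44 | 164 | 0–3 | 4 |
| 45 | 165 | 0–2 | 3 |
| 46 | 166 | 0–1 | 2 |
| 47 | 167 | 0 | 1 |
| 48 or more | 168 or more | none | 0 |

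Only entry ages 42 to 47 days are affected. Each of these infants can reach 168 days by using 1 to 6 of the 28 available days.

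**2. The interval after dose 4 (days counted from Visit 4)**

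Inputs: Visit 5 at D30 to D51 (protocol window); the 6-month call (TC6) at D180 to D210. The tables count 5 visits and, separately, 6 telephone calls, so TC6 is read as a call and Visit 5 as the next visit.

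- D31 to Visit 5: 0 days if Visit 5 is on D30, and 51 − 30 = 21 days if it is on D51.
- D31 to TC6: 180 − 30 = 150 days to 210 − 30 = 180 days.
- The interval as labelled is therefore at most 21/150 = 14% of the time from D31 to TC6.
- Visit 5 to TC6: from 180 − 51 = 129 days to 210 − 30 = 180 days. This time is in no per-dose interval.

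Events in those days are in the whole-study row by group. Table 5.2 reports percentages of subjects with an event. The late period cannot be obtained by subtracting the per-dose percentages from the whole-study percentage, because one subject can have events in several intervals.

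**The case against.** On the age row: it is labelled approximate, the column header points to the footnote, and the footnote is worded as a requirement. The visit intervals alone allow 162 to 237 days, beyond the limits at both ends, so sites must work from the footnote in any case. All of this stands, and it keeps the point small. It does not make 164 right: a row that matches the footnote exactly at 224 should match it at 168. A reader might infer that the plan permits hepatitis B dosing below 24 weeks, or that a measurable number of infants will be dosed early. The documents support neither. The footnote forbids it, and no distribution of entry ages is given from which a rate could be worked out.

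On Table 5.2 the opposing case is stronger. A collection period is not a required analysis interval. SAP 4.2.1.3 and 4.2.1.4 ask for 7-day, 30-day and whole-study periods, and none of these is a per-dose period from D31. Table 5.2 is introduced as a minimum. The label also matches the diary card, which runs from Visit 4 to Visit 5; by the table footnote the memory aid takes over from Visit 5. The SAP does not define the next visit, and the protocol's TC6 steps loosely call that contact a visit, although the separate counts of visits and calls make Visit 5 the likelier reading. A reader might infer that events in the 6-month follow-up go uncollected or unanalysed, or that the table contradicts the SAP. Neither is so: the whole-study rows include every such event by group. What remains is that the late period is not shown separately.

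**Conclusion.** The lower limit in the Visit 3 age row is wrong as written, by 4 days, in both documents. The error is minor. It could matter only for infants enrolled at 42 to 47 days, and only if someone worked from the row instead of the footnote. The enumeration assumes that every visit falls inside its stated window.

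The dose 4 interval in SAP Table 5.2 is not an error. It covers 0 to 21 days under the protocol window and leaves 129 to 180 days visible only within the whole-study total. Showing that period separately is a worthwhile improvement in a trial whose sole purpose is safety. This rests on reading the next visit after dose 4 as Visit 5. No data are lost, no group comparison is biased, and no sample-size figure is touched.

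The +14 versus +21 difference for Visit 5 is clerical.

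**What to change.** 1. Change the Visit 3 age row to 168 to 224 days in the protocol's Table of Study Procedures and in SAP Table 3.3, and confirm that no site tool or window check uses 164. Cost: one figure in two tables.
2. In the SAE/AESI and MAAE rows of SAP Table 5.2, let the dose 4 interval run from D31 to the 6-month contact (TC6). The other doses, the whole-study rows and the row for AEs leading to discontinuation can stay as they are. Cost: slightly more or changed table output, and no new data.
3. Correct the Visit 5 window in SAP Table 3.3 from +14 to +21 days. Cost: one cell.

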1.1 Background

This study (MET41) will evaluate the safety of a 4-dose series of the quadrivalent Meningococcal Polysaccharide (Serogroups A, C, Y, and W) Tetanus Toxoid Conjugate Vaccine (hereafter referred to as MenACYW conjugate vaccine) in children starting immunization at 6 weeks of age. The purpose of the MET41 study is to demonstrate that the safety profile of the MenACYW conjugate vaccine is similar to that of MENVEO[®] when administered concomitantly with routine pediatric vaccines given to healthy infants and toddlers in the United States (US) and Puerto Rico.

Invasive meningococcal disease (IMD) is a serious illness caused by the bacterium N. meningitidis, a Gram-negative diplococcus found exclusively in humans. Symptoms may include intense headache, fever, nausea, vomiting, photophobia, stiff neck, lethargy, myalgia, and a characteristic petechial rash (1). At least 12 different meningococcal serogroups have been classified based on the immunochemistry of the capsular polysaccharides (PS). Some strains are more likely than others to cause infection (1)(2)(3). Worldwide, most cases of meningococcal disease are caused by serogroups A, B, C, X, Y, and W (2) (3) (4). Serogroup B is responsible for endemic disease and some outbreaks, while serogroup C is responsible for large outbreaks (5). Serogroup A remains the main cause of epidemics in the world and is especially dominant in Africa and Asia. Serogroup W has been observed in Africa, as well as the United Kingdom, in residents who participated in the Hajj pilgrimage to the Kingdom of Saudi Arabia (4) (6) (7) and more recently in Chile (8), Turkey (9) (10), China (11) (12), Argentina (13), Brazil (14) (15), and other parts of the world. Serogroup X causes substantial meningococcal disease in parts of Africa, but rarely causes disease in other parts of the world (2) (16). Serogroup Y has not been associated with outbreaks, but the frequency with which it causes sporadic cases has gradually increased in the US and more recently in Canada and Europe (17) (18) (19). The Y serogroup is commonly associated with meningococcal pneumonia, particularly in older adults ≥ 65 years of age (20). Outbreaks of serogroup B meningococcal disease have also been reported on college campuses in the US during the last five-year period: a prolonged outbreak of serogroup B on a university campus in Ohio from 2008 – 2010 and 2 universities in New Jersey and California in 2013 (21) (22).

The epidemiology of *N. meningitidis* can be described as complex, unpredictable, geographically variable, and changing over time. Meningococcal disease occurs worldwide in both endemic and epidemic forms with seasonal variation. In Europe, the incidence rate of IMD has remained stable over the last 5 to 10 years, with the highest peak occurring in the population less than 4 years of age and a smaller peak in the 15 to 19 year old group. The highest incidence rate in Europe is caused by serogroup B, followed by C (23). The highest proportion of meningococcal cases was due to serogroup B in the population under 5 years of age. The highest proportion of serogroup C cases was observed in the population 25 to 44 years of age while the proportion of serogroup Y cases was highest in the population aged 65 years and above.

Surveillance data from England and Wales showed an increase in endemic meningococcal serogroup W disease across all age groups, accounting for 15% of all IMD cases in 2013 - 2014 compared with an average of 1% to 2% of all IMD cases in earlier years (24). A gradual increase

in serogroup Y IMD has also been recently reported in England and Wales between 2007-2009 (25) and in Sweden during 2005 - 2012 (26) (27). Nearly 50% of all IMD in Sweden was caused by serogroup Y in 2012 (26). Similarly, an increase in the proportion of IMD caused by serogroup Y has been observed in other Nordic countries, accounting for 31% in Norway in 2009 - 2010 (28) and 38% in Finland in 2010 (29).

In the US, the incidence rate of IMD was 0.14 per 100,000 in all ages; 0.83 per 100,000 in infants less than 1 year; 0.62 per 100,000 in toddlers 1 year of age; 0.27 per 100,000 in children 2 to 4 years of age; and 0.02 per 100,000 in children 5 to 17 years of age in 2013. The age specific incidence rate per 100,000 was 0.08 in adults 50 to 64 years of age, 0.03 in adults 65 to 74 years of age, 0.14 in adults 75 to 84 years of age, and 0.43 in adults 85 years of age and older in 2013 (30). Serogroups B, C, and Y are the major causes of meningococcal disease in the US, each being responsible for approximately one-third of the overall cases. The proportion of cases caused by each serogroup varies by age group. Serogroups C, W, or Y, which are included in vaccines available in the US, cause 73% of all cases of meningococcal disease among persons 11 years of age or older (31). Approximately 60% of disease among children aged 0 through 59 months is caused by serogroup B, for which no conjugate vaccine is licensed or available in the US. More than 50% of meningococcal disease in children 0 to 6 months of age is caused by serogroup B; serogroup Y is also more prevalent in this age group (20).

The goal for MenACYW conjugate vaccine is to provide broad protection against IMD caused by serogroups A, C, Y, and W in all age groups including children as young as 6 weeks of age, adolescents, and adults, including those 56 years of age and older.

